**A Mechanistic Perspective on Post-Activation Performance
Enhancement Responsiveness: A Randomized Controlled
Study of Acute Changes in Muscle Architecture, Contractile
Property Kinetics, and Muscle Excitability**

NCT06982937

18.05.2025

Objectives and endpoints.

The primary objective is to test whether a heavy conditioning activity (CA; one set of 2–3 repetitions at ~90% 1RM) produces post-activation performance enhancement (PAPE) in countermovement jump (CMJ) height compared with a control treadmill warm-up within the 4–12 min window after the intervention. The analysis does not assume *a priori* when the maximal effect occurs; instead, the minute of maximal between-group difference (denoted T^*) will be identified empirically. The primary endpoint is the change in CMJ height from baseline (ΔCMJ) at post-intervention time points (4, 6, 8, 10, 12 min). Secondary endpoints include the time-course of ΔCMJ within the experimental group (EXP), individual responder status at each time point, and the associations between neuromuscular phenotype—estimated as %MHC-I from tensiomyography (TMG)—and the magnitude, timing, and likelihood of response. Ultrasound (USG) morphology (muscle thickness, pennation angle, derived fascicle length) will be analysed in parallel to performance endpoints. Electromyography (EMG), where available, will be treated analogously to USG/TMG (see below).

Data handling and derived variables.

At each time point, CMJ height is the mean of three trials; ΔCMJ and percentage change (% ΔCMJ) will be computed relative to baseline. Individual response is classified using MDC. USG outcomes will be averaged across three images; fascicle length is calculated as thickness divided by the sine of pennation angle (degrees converted to radians). TMG-based %MHC-I is estimated from delay, contraction, and half-relaxation times using the published multivariable model; TMG amplitudes and time constants may also be expressed as Δ or % Δ . If EMG is collected, signals will be band-pass filtered, rectified, quantified with 50-ms RMS, normalized (to MVC or M-wave), and summarized over task-relevant phases; % Δ at 4–12 min is computed analogously. Values >3.5 SD from group-time means will be flagged; primary analyses include all data, with winsorized sensitivity checks reported only if inferences change. Missing data will be not imputed for the primary analysis; mixed-effects models accommodate missingness assuming MAR.

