Primary analysis and identification of the peak time (T^*).

The confirmatory analysis uses a RM-ANOVA with ΔCMJ as the outcome, Group (EXP vs CON), Time (time effect: 4, 6, 8, 10, 12 min), and Group \times Time. If the interaction is significant, we estimate adjusted between-group contrasts at each minute with Bonferroni correction across the five time points. T^* is defined as the minute showing the largest positive EXP–CON difference in estimated marginal means (EMMs) with the smallest p-value. We report the EMM difference at T^* (95% CI) and effect size (d’Cohen). Greenhouse–Geisser correction if needed.

Within-group time-course and kinetics.

To describe the temporal profile without prespecifying a target minute, we analyse ΔCMJ across time within EXP using a one-way repeated-measures ANOVA (or LMM if assumptions are violated), followed by Bonferroni-adjusted pairwise EMMs to locate the within-group peak. To characterise response timing at the individual level, we model time to first and time to peak response (4–12 min) using Kaplan–Meier curves with censoring at 12 min, compare strata by log-rank tests, and fit Cox proportional-hazards models to estimate hazard ratios (HR, 95% CI) and concordance (C-index). This kinetics framework provides an assumption-light estimate of when athletes typically express PAPE.

Responder analyses and discrimination.

Responder distributions (Positive/neutral/adverse) will be compared between EXP and CON at each minute using likelihood χ^2 test. For mechanistic discrimination at specific minutes (including T^* once identified), we fit logistic models with %MHC-I as a continuous predictor and report ORs (95% CI),

Nagelkerke R², AIC, Hosmer–Lemeshow calibration, and ROC-AUC with sensitivity, specificity, and Youden's J cut-offs. Moderation analysis also will be used with simple slope analysis.

Phenotype and morphology linkages (USG/TMG/EMG).

Associations between %MHC-I and Δ CMJ will be quantified at each minute using Pearson's r. USG variables (thickness, pennation angle, fascicle length) will be analysed with the same three lenses applied to performance: (i) within-EXP time-course (rmANOVA/LMM with Tukey), (ii) responder linkage at each minute (one-way ANOVA or robust alternative; Hedges' g for P vs X), and (iii) phenotype linkage (correlations and moderation models). TMG (e.g., Dm, Tc, Tr) and EMG (e.g., normalized RMS, median frequency) follow this identical framework to ensure coherence across modalities.

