Moderation and mediation (pre-specified).

All moderators and predictors will be mean-centered; multicollinearity is checked (VIF < 5). Primary moderation models test whether (a) baseline CMJ modifies the effect of %MHC-I on Δ CMJ and (b) baseline morphology (thickness, pennation angle, fascicle length) modifies the effect of baseline CMJ on Δ CMJ. Significant interactions will be decomposed with simple slopes at -1 SD, mean, and +1 SD, with 95% CIs via nonparametric bootstrap (1,000 resamples) and publication-ready interaction plots. Exploratory mediation tests whether acute morphological change (e.g., % Δ thickness at a given minute) transmits baseline morphology effects to % Δ CMJ; indirect, direct, and total effects will be estimated by bootstrap (5,000 resamples; bias-corrected CIs) and interpreted cautiously.

Assumptions, multiplicity, and robustness.

Model diagnostics include residual normality (Shapiro–Wilk), homoscedasticity (residual–fitted patterns, Breusch–Pagan), linearity, and independence by design. Sphericity is tested for rmANOVA (Mauchly) with Greenhouse–Geisser corrections as needed. If mechanistic variables are skewed, appropriate transformations (e.g., log for EMG amplitude) are considered; otherwise we rely on LMM robustness. Multiplicity is controlled via Holm across the five between-group contrasts, FDR for correlation families, and restraint in post-hoc testing; moderation/mediation will be estimation-focused with full interval reporting and are not used to redefine the primary inference.

Reporting, visualization, and software.

We report means \pm SD with 95% CIs; between-group effects as Hedges' g; within-subject effects as d_{nZ} ; ANOVA-style effects as η^2 ; logistic results as ORs with AUC; and survival results as HRs with concordance. Figures include EMM trajectories with 95% CIs, individual waterfall plots with MDC bands, ROC curves for %MHC-I, Kaplan–Meier curves for first/peak response, interaction plots for significant moderations, and path diagrams for supported mediations. Analyses will be performed in Jamovi 2.6 and STATISTICA 13.1.

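### The Youden cut-off for %MHC-I is chosen and evaluated on the same data, at minutes not listed in advance and without internal validation, so its apparent accuracy is biased upward

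*Combined protocol and SAP*

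**What the plan says.** All places are in the combined protocol and SAP.

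- **Outcome.** Under Data handling and derived variables: "Individual response is classified using MDC". Neither the MDC value nor an expected responder rate is given.
- **Model and minutes.** Under Responder analyses and discrimination: "For mechanistic discrimination at specific minutes (including T^* once identified), we fit logistic models with %MHC-I as a continuous predictor". Apart from T^*, the minutes are not named.
- **Measures.** The same section lists "ROC-AUC with sensitivity, specificity, and Youden's J cut-offs" beside the odds ratio with its 95% CI and fit and calibration statistics. It names no pre-set cut-off, hold-out set, cross-validation or optimism correction.
- **Choice of T^*.** Under Primary analysis and identification of the peak time: "T^* is defined as the minute showing the largest positive EXP–CON difference in estimated marginal means (EMMs) with the smallest p-value". The AUC of %MHC-I plays no part.
- **Resampling.** Under Moderation and mediation, simple slopes are reported "with 95% CIs via nonparametric bootstrap (1,000 resamples"), and mediation effects use 5,000 resamples. The ROC results are not bootstrapped.
- **Multiplicity and reporting.** Under Assumptions, multiplicity, and robustness, named adjustments cover the five between-group contrasts and the correlation families, not AUCs or cut-offs. Under Reporting, visualization, and software, the planned figures include "ROC curves for %MHC-I", and no interval is stated for the AUC, the cut-off, or its sensitivity and specificity.

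**The concern.** Two things are tuned to the data and then judged on the same data: the direction of the rule (whether high or low %MHC-I predicts response) and the threshold. Both choices favour the rule, so the reported sensitivity, specificity and J are on average better than the rule would achieve in new athletes. The AUC of a single predictor is affected only through the choice of direction.

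The relation of %MHC-I to the likelihood of response is a stated secondary endpoint, and a cut-off is the result that readers are most likely to reuse. Without a correction or an interval, they cannot tell a real threshold from a sampling artefact. Because the minutes are not listed, nothing in the text prevents emphasis on the most favourable one.

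**Working it through.** The plan states no sample size, AUC or cut-off, so there is no figure to reproduce. The check asks what the planned procedure returns when %MHC-I carries no information (true AUC 0.50, true J 0).

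**Assumptions, none from the documents.** N, the number in the logistic model, is 20 to 200. Responders (positive against the rest) make up 30–50%. Where several minutes are involved, the latent correlation between minutes is 0.5 or 0.8 and responders are about 40%.

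**Formulas.** J = sensitivity + specificity − 1, maximised over all thresholds in the fitted direction. The direction-free AUC is max(A, 1 − A). With n1 responders and n0 non-responders, the null standard error of A is √[(N + 1)/(12·n1·n0)], and the mean of the direction-free AUC is approximately 0.5 + SE·√(2/π).

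**Closed-form check of the AUC.**
- N = 20, n1 = 6, n0 = 14: SE = √(21/1008) = 0.144; mean ≈ 0.5 + 0.144 × 0.798 = 0.615.
- N = 60, n1 = n0 = 30: SE = √(61/10800) = 0.075; mean ≈ 0.5 + 0.075 × 0.798 = 0.560.

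Simulation gives 0.617 and 0.560.

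**Step 1: one fixed minute, useless predictor, 10,000 runs per setting.**

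| N | Mean direction-free AUC | AUC ≥ 0.70 | Mean apparent J |
|---|---|---|---|
| 20 | 0.61–0.62 | 14–19% | 0.34–0.38 |
| 30 | 0.59 | 6–8% | 0.29–0.32 |
| 60 | 0.56–0.57 | about 1% | 0.21–0.23 |
| 100 | 0.55 | ≤ 0.2% | 0.16–0.18 |
| 200 | 0.53–0.54 | 0% | 0.12–0.13 |

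Sensitivity and specificity average (1 + J)/2. At N = 20 that is (1 + 0.34)/2 = 0.67 to (1 + 0.38)/2 = 0.69 for a rule worth 0.50. With the direction fixed in advance, the mean AUC was 0.50 at every N, so its bias comes only from the choice of direction. J is biased at every N checked.

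**Step 2: does T^* add to this?** Five correlated minutes, 5,000 runs, N = 20, correlation 0.5. At T^*, mean AUC is 0.610 and J 0.357. At a fixed minute they are 0.614 and 0.367. T^* adds nothing.

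**Step 3: what if the minute with the best AUC were highlighted?** This is not a planned procedure.
- N = 20: mean AUC 0.70–0.71, with AUC ≥ 0.70 in 44–53% of trials.
- N = 30: 0.66–0.67 and 24–29%.
- N = 60: 0.61–0.62 and 3–5%.

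**Step 4: does the remedy work?** Corrected value = apparent value − mean over resamples of (performance of the resample's rule in the resample − performance of that rule in the original data), with direction and cut-off re-selected each time. 300 data sets of 100 resamples, 40% responders.

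| N | AUC apparent → corrected | J apparent → corrected |
|---|---|---|
| 20 | 0.61 → 0.54 | 0.36 → 0.15 |
| 30 | 0.58 → 0.51 | 0.28 → 0.09 |
| 60 | 0.56 → 0.52 | 0.21 → 0.07 |

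Most of the bias goes. Some of the bias in J remains.

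**The case against.** The strongest defence is that the plan already reports an odds ratio with a 95% CI from the same model. In a null simulation at N = 20, that interval excluded 1 in about 2% of trials, and among trials with AUC ≥ 0.70 it still included 1 in 84–90%. A careful reader would therefore usually see an inconclusive result next to the AUC. This stands as a partial safeguard. It is weaker at N = 30, where 6–8% of trials reach AUC 0.70 and about 3% do so with an interval excluding 1. At no N does it correct the cut-off or its sensitivity and specificity.

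The defence can also say that the section frames the analysis as mechanistic, not as a selection tool, and that it is secondary. Both are true and limit the consequences, but not the bias.

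Three stronger readings are tempting, and the documents do not support them:
- **That evaluating at T^* inflates the AUC.** T^* is chosen on the between-group mean difference, and step 2 shows no added optimism.
- **That a useless predictor will look discriminating.** At a single minute and N = 20, 81–86% of null trials stay below AUC 0.70. The higher best-of-five figures describe selective emphasis that the plan leaves open but does not prescribe.
- **That the sample is small.** No sample size is given, and the size of the bias depends on it.

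**Conclusion.** The point holds in a limited form. Followed as written, the plan gives upward-biased values of J, and of sensitivity and specificity taken together, at minutes not fixed in advance, with no validation and no stated interval for the AUC. For N of 20 to 60 and 30–50% responders, both assumed, the mean apparent J of a worthless predictor is about 0.2 to 0.4 and its mean direction-free AUC about 0.56 to 0.62. At N = 200 the J bias is still 0.12–0.13. These figures are for an exactly null predictor. That the bias exists follows from the method itself; its size in this trial cannot be known from the documents. Further inflation, to a mean AUC of about 0.71 at N = 20, arises only if the best-looking minute is singled out. The primary inference is unaffected.

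**What to change.** In Responder analyses and discrimination:

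1. Replace the open reference to specific minutes with a commitment to report discrimination at all five (4, 6, 8, 10 and 12 min).
2. Report each AUC with a 95% CI.
3. Report bootstrap optimism-corrected AUC, sensitivity, specificity and J beside the apparent values, re-selecting direction and cut-off in every resample. T^* need not be re-selected for this purpose.
4. Label the cut-offs exploratory, and say that the corrected J can still be somewhat optimistic.
5. Only if a minute is singled out because of its AUC, add a permutation p-value for the maximum AUC over the five minutes.

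This is a cheap improvement that needs no new data. The costs are a short script outside the two named packages (Jamovi and STATISTICA) and less favourable reported values.

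### The %MHC-I link with ΔCMJ is assessed minute by minute with no test that it differs between minutes, so the planned correlations cannot support a time-specific phenotype claim

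*Combined protocol and SAP*

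**What the plan says.** Under Objectives and endpoints, a secondary endpoint is the association of %MHC-I with "the magnitude, timing, and likelihood of response". Three later sections bear on it.

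- **Phenotype and morphology linkages:** "Associations between %MHC-I and Δ CMJ will be quantified at each minute", using Pearson's r. The minutes are those of the primary model, "Time (time effect: 4, 6, 8, 10, 12 min".
- **Responder analyses and discrimination:** logistic models with %MHC-I as predictor, fitted at particular minutes, including the empirically chosen peak.
- **Within-group time-course and kinetics:** Kaplan–Meier curves, log-rank tests and Cox models for time to first and time to peak response. No strata or covariates are named.

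Multiplicity for the correlations is handled by "FDR for correlation families"; neither the procedure nor the family is defined.

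Three interactions are specified: Group × Time in the primary analysis, and baseline CMJ × %MHC-I and baseline morphology × baseline CMJ under Moderation and mediation. A general sentence on moderation in the responder section names no moderator. No %MHC-I × Time term, comparison of dependent correlations or time-averaged association appears.

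**The concern.** A statement that the phenotype matters at one minute and not at another concerns a difference between two associations. Five separate tests against zero do not address that difference. FDR control limits false associations; it does not limit false differences between associations.

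The plan already follows the right principle for its primary outcome, where per-minute contrasts depend on the interaction: "If the interaction is significant, we estimate adjusted between-group contrasts". The phenotype analysis has no such step.

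At stake is a mechanistic conclusion about when athletes of a given fibre type respond. A constant link tested with modest power at each minute can give significant and non-significant minutes by chance, and the plan has no test to tell this apart from a real change over time.

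**Working it through.** The documents state no sample size, alpha, effect size or power, so there is no planned figure to reproduce. The size has to come from assumed inputs.

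**Inputs**
- Five minutes (Primary analysis section).
- FDR (Assumptions, multiplicity, and robustness); assumed to be Benjamini–Hochberg (BH) over the five minutes.
- Two-sided alpha of 0.05: assumed.
- N: assumed. The plan also does not say whether the correlations use EXP only or both groups.
- True r between %MHC-I and ΔCMJ: assumed, and equal at all five minutes.
- Correlation c of ΔCMJ between minutes: assumed. A common baseline ("ΔCMJ and percentage change (% ΔCMJ) will be computed relative to baseline") makes positive values likely.

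**Step 1. Power at one minute.** By Fisher's z, power ≈ Φ(atanh(r)·√(N−3) − 1.96). For r = 0.4 and N = 20: atanh(0.4) = 0.424, √17 = 4.123, product 1.747; 1.747 − 1.96 = −0.213; Φ(−0.213) ≈ 0.42. The same formula gives 31% at N = 15, 60% at N = 30 and 73% at N = 40. With power in this range, some minutes will often pass and others fail although all five links are equal.

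**Step 2. Mixed patterns under a constant link.** Five ΔCMJ values per athlete were simulated with equal true r, equal variances and exchangeable correlation c. Each minute was tested by Pearson's r with BH. A mixed pattern is 1 to 4 of the 5 minutes significant. The comparator is the %MHC-I × Time F test with Greenhouse–Geisser correction.

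| N = 20, r = 0.4 | Mixed pattern after BH | False %MHC-I × Time signal |
|---|---|---|
| c = 0.6 | 38% | 3–5% |
| c = 0.8 | 22% | 3–5% |
| c = 0.9 | 12% | 3–5% |
| c = 0.95 | 5% | 3–5% |

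At c = 0.6 about 51% of trials have at least one significant minute, so 38/51 ≈ 75% of those show a mixed pattern.

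**Step 3. Where it fades.** At N = 60 and r = 0.5 the mixed-pattern rate is 1–6%.

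**Step 4. Power of the alternatives.** Under a constant link (N = 20, r = 0.4, c = 0.6), one test on the 4–12 min average has 61% power, against 51% for any minute after BH. The order reverses if the link changes. With r falling 0.5, 0.4, 0.3, 0.2, 0.1 (N = 20, c = 0.6), the average test has about 37%, any minute after BH about 49%, and the interaction test about 33%.

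**The case against.** **The plan has a timing analysis.** It does: Kaplan–Meier and Cox. A reader might infer that timing rests on the correlations alone, which the documents do not support. But %MHC-I is not named in the Cox analysis, and a hazard model concerns when a response occurs, not whether the ΔCMJ slope on %MHC-I varies between minutes.

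**The plan says only that associations are quantified.** This stands. A reader might infer that a constant effect will often be reported as time-specific. No section says that significance at one minute but not another will be read as a timing difference. What can be said is that timing is an endpoint, significance testing is implied by the FDR control, and no rule prevents that reading.

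**The two rates are not like for like.** This also stands. With a constant non-zero r, each significant minute is a true association. A mixed pattern reflects limited power and becomes an error only when it is read as a difference. The 3–5% is the type I error of a test that asks the timing question directly.

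**The rate depends on assumed inputs.** Agreed. CMJ at each time point is the mean of three trials and every change shares one baseline, so high between-minute correlations, with low mixed-pattern rates, are plausible.

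**A single averaged test is not always stronger.** Correct, as step 4 shows. The plan does not presume when the effect peaks, so constancy cannot be taken as its premise.

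**Conclusion.** The gap is real and does not depend on the simulation: an endpoint covers phenotype and timing, and no planned analysis tests whether the %MHC-I–ΔCMJ link differs between minutes. Per-minute significance, with or without FDR, cannot fill it.

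The size is uncertain. At N = 20 and a constant r of 0.4, mixed patterns occur in about 5% to 38% of trials for between-minute correlations of 0.95 down to 0.6, against 3–5% for a direct interaction test. They are rarer with a large N and a strong r. All of these inputs are assumed. The documents do not support a statement that mixed patterns will be common in this trial, nor that they will be misreported. A general gain in power from a single model is not established either.

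The endpoint is secondary, so the change should be made, but the primary inference is not affected.

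**What to change.** Add one repeated-measures or mixed model of ΔCMJ on baseline %MHC-I, Time and %MHC-I × Time, Greenhouse–Geisser corrected or with unstructured covariance. State that the %MHC-I value used is the baseline one, since the plan does not say when it is measured. Fit the model in EXP, or in both groups with Group and its interactions included; pooled without Group, it would not isolate response to the conditioning activity.

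- Report the time-averaged slope for magnitude.
- Report the interaction, with estimates and confidence intervals, for timing.
- Keep the five FDR-adjusted correlations and the per-minute logistic models as descriptive.
- Say that the link differs between minutes only if the interaction supports it.
- Name %MHC-I as the covariate in the Cox model for time to response.

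The cost is SAP wording and one extra model of a kind already planned; no new data are needed. There are two downsides. The interaction test is weak in a small sample (about 33% power in the declining-r case above), so a non-significant result does not show constancy. The time-averaged slope also loses power against per-minute tests if the link is confined to some minutes.

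### Ultrasound, TMG and EMG changes get a within-EXP time test but no EXP–CON comparison, so a planned time effect cannot be separated from drift shared with the treadmill arm

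*Combined protocol and SAP*

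**What the plan says.** The title calls the trial a randomised controlled "Study of Acute Changes in Muscle Architecture, Contractile" property kinetics and muscle excitability. Under Objectives and endpoints, ultrasound morphology "will be analysed in parallel to performance endpoints", and EMG, where available, is to be handled like ultrasound and TMG.

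The section on phenotype and morphology linkages defines the analysis. Ultrasound variables "will be analysed with the same three lenses applied to performance: (i) within-EXP time-course (rmANOVA/LMM with Tukey), (ii) responder linkage at each minute" and, third, a phenotype linkage by correlations and moderation models. TMG and EMG "follow this identical framework to ensure coherence across modalities".

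Explicit between-group tests appear in two places, both for CMJ-derived outcomes:
- In the primary analysis section: "The confirmatory analysis uses a RM-ANOVA with ΔCMJ as the outcome, Group (EXP vs CON"), with Time and their interaction.
- In the responder section: "Responder distributions (Positive/neutral/adverse) will be compared between EXP and CON at each minute".

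On scale, the data-handling section says "TMG amplitudes and time constants may also be expressed as Δ or % Δ" and gives EMG a percentage change over 4–12 min. The mediation paragraph names percentage change in thickness. No scale is stated for the ultrasound time-course.

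**The concern.** A within-group time-course in a randomised trial sets the control arm aside. Anything that moves both arms alike, such as repeated jumping or repeated stimulation, enters the EXP time effect together with any effect of the conditioning activity (CA). The EXP data alone cannot separate the two. A reader of the report could take a significant within-EXP change in thickness, pennation angle or contraction time as a mechanism of the CA, when the same change may have occurred after the treadmill warm-up.

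At stake is how the mechanistic results are interpreted. The primary test of ΔCMJ has its own Group factor and is not touched.

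**Working it through.** **Step 1: text check.** Each analysis that involves ultrasound, TMG or EMG is set against the question of whether it compares EXP with CON on that measure.

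| Analysis | What is compared | EXP–CON test of the measure? |
|---|---|---|
| Lens (i), time-course | Times within EXP | No |
| Lens (ii), responder linkage | Responder classes, not randomised groups | No |
| Lens (iii), phenotype linkage | Correlations and moderation; no Group term named | No |
| Mediation | Starts from baseline morphology; outcome is percentage change in CMJ | No |

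The multiplicity rule agrees: "Multiplicity is controlled via Holm across the five between-group contrasts". Five is the number of CMJ minutes, and no family of contrasts is given for the mechanistic measures.

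**Step 2: algebra.** Write a measurement on person i at time j as Y_ij = a_i + d_j + c_j + e_ij in EXP, and the same without c_j in CON. Here d_j is drift common to both arms and c_j is the CA effect relative to control, both zero at baseline.
- Within EXP, only the sum d_j + c_j can be estimated. Shared drift and a CA effect of the same shape give identical EXP data.
- On change scores D_ij = Y_ij − Y_i0, baseline cancels between minutes: D_ij − D_ik = Y_ij − Y_ik. The Time test and pairwise comparisons therefore compare minutes only with each other. On percentage change, baseline remains only as a divisor, 100(Y_ij − Y_ik)/Y_i0.
- On change scores, if d_j + c_j is constant over 4–12 min, Time has nothing to detect. If d_j varies, Time detects it even when every c_j is zero.
- The EXP–CON difference at minute j has expectation c_j. Common drift cancels.

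**Step 3: size, by simulation.** The documents give no sample size, SD, reliability or drift, so every input is an assumption and there is no figure in the plan to reproduce.
- n = 12/20/30 per arm; baseline plus 4, 6, 8, 10 and 12 min; two-sided 0.05; 20,000 data sets per setting.
- Error SD 1 and person SD 3, so reliability = 9/(9 + 1) = 0.90; independent errors.
- Shift = 0.5 SD of a difference score = 0.5 × √2 = 0.71. The decaying form multiplies it by 1, 0.75, 0.5, 0.25 and 0 at the five minutes.
- The smaller shift is 0.5 error SD, that is 0.5/√2 = 0.35 SD of a difference score.
- The averaged EXP–CON contrast is the ANCOVA of the mean post value on Group and baseline.

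Percentage of data sets with a significant result, on change scores for the within-EXP test:

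| Setting | Within-EXP Time | EXP–CON, averaged |
|---|---|---|
| Shared decaying drift, no CA effect | 27/46/66 | about 5 |
| Same, smaller shift | 15/24/36 | about 5 |
| Shared constant drift, no CA effect | 5/5/5 | about 5 |
| Constant CA effect, no drift | 5/5/5 | 34/54/72 |
| Decaying CA effect, no drift | 27/46/66 | 12/18/25 |

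The first and last rows have the same within-EXP figures because the EXP data are the same in both; only CON tells them apart. Under a constant CA effect the Group × Time test also stays at 5/5/5.

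With Greenhouse–Geisser correction the first row becomes 20/41/64. With AR(1) errors (correlation 0.5) and that correction it becomes 29/51/71, and the EXP–CON contrast stays at 4.9–5.2.

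For the responder linkage (n = 20), a one-way ANOVA by responder category rejects in 5.0% with and without common drift.

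**The case against.** **No endpoint promises this test.** The primary objective concerns CMJ height. The secondary endpoints are the EXP time-course of ΔCMJ, responder status and links with fibre-type phenotype. The title also opens with responsiveness, which lenses (ii) and (iii) address. This stands: a reader might infer that the plan fails to analyse a declared endpoint, and the documents do not support that. No sentence attributes mechanistic change to the CA either. The gap lies between the title and the tests specified.

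**A constant effect would not be wholly hidden.** It is tempting to say that it would be invisible. That is true only of the Time test and the pairwise minutes. The reporting section also commits to means with 95% confidence intervals. In the constant-effect setting above, at least one minute's unadjusted interval for mean change excludes zero in about 71/89/97% of data sets. This stands as a limit on the concern, but those intervals are uncontrolled and would behave identically under constant shared drift.

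**The scale matters.** If baseline were a level of the ANOVA, constant shared drift alone would give 33/56/77%, and a reader might take that as the size of the problem. The text points the other way: the ultrasound lenses are said to match those for performance, which uses ΔCMJ; EMG has a percentage-change scale; and percentage change in thickness is named. On change scores constant drift does no harm, and the false-positive concern narrows to drift that varies over 4–12 min.

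**General wording might cover it.** The statement about parallel analysis, the Holm rule and the convention of reporting between-group effects as Hedges' g could be read as implying a group comparison. None names one for a mechanistic measure, and the section that spells out the lenses omits it.

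**CON may not have been measured.** The documents do not say. The outlier rule refers to means by group and time, which hints at CON data without establishing them.

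**Conclusion.** The point holds in limited form. The plan specifies no randomised comparison of the acute ultrasound, TMG or EMG changes named in the title, and its only time-course test for them cannot distinguish a CA effect from drift shared with the treadmill arm. This follows from the text and the algebra, without any assumed number.

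The size does rest on assumptions. With decaying shared drift and no CA effect, the within-EXP test on change scores is significant in about 27/46/66% for 12/20/30 per arm, or 15/24/36% for the smaller shift. These figures illustrate the mechanism and do not estimate what will happen in this trial.

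A reader might infer that the whole mechanistic programme is compromised. It is not: additive drift common to all participants does not disturb the responder or phenotype linkages, and the confirmatory ΔCMJ analysis is unaffected. The change is worth making because the report is likely to be read as controlled evidence on mechanism.

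**What to change.** 1. For each ultrasound, TMG and EMG variable measured in both arms, add a secondary or exploratory mixed model with Group, Time, Group × Time and the baseline value as covariate.
2. Base any claim of CA-related mechanistic change on the EXP–CON contrasts from that model, averaged over 4–12 min and by minute with Holm, worded as CA versus treadmill warm-up. Do not rely on Group × Time alone, because a constant CA effect produces no interaction on post-baseline values.
3. Label within-EXP time-courses as descriptive, and state for each measure whether baseline is an ANOVA level or change scores are used.
4. Where a measure was not taken in CON, state that its change cannot be attributed to the CA.

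The cost is SAP wording and a few extra models. No new data are needed if CON was measured; if it was not, only items 3 and 4 apply. There is some loss of sensitivity: for a CA effect that decays over 4–12 min without drift, the controlled contrast detects about 12/18/25% (averaged) or 13/22/34% (any minute, Holm), against 27/46/66% for the uncontrolled test, under the same assumed inputs. That extra sensitivity has a price, since the uncontrolled test responds equally to drift.
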